6. METHODS

The study will consist of the following steps, replicating the Yale ADP methods:

- (1) Recruitment;
- (2) Pre-screening: Brief telephone or in-person to determine eligibility for full screening beginning with establishing non-treatment seeking status;
- (3) Full Screening/baseline visit: 1-2 in-person visits to obtain consent and to evaluate eligibility (e.g. to reject participants with medical conditions): a *diagnosis of AUD* and *heavy drinking criteria*, and by confirming that the individual is *non-treatment seeking*. If these criteria are met, physical examination and laboratory testing will be conducted. Eligible participants then proceed to
- (4) Human Lab ADP Sessions 1, 2, and 3, in which participants will receive a single dose of lacosamide 100 mg, lacosamide 200 mg, or placebo. The order of medications will be randomly assigned and counterbalanced across participants. Between each session, there is a 7-day washout period when no study medication is given.
- (5) The day following each ADP Session, a study staff member will call the participant to ask about well-being, assess for adverse effects and collect drinking data.
- (6) Participants then undergo a 1-week Follow-up visit, where adverse events and alcohol use will be assessed and a research clinician will provide a motivational enhancement session to encourage these non-treatment seeking participants to consider treatment and provided with referral materials.

6.1 Treatment – Drug

6.1.1 Identity of Investigational Product

Lacosamide (LAC) is a functionalized amino acid analogue of D-serine, and is FDA-approved as an anticonvulsant for the treatment of partial-onset seizures. The pharmacokinetic profile of LAC indicates it is rapidly and completely absorbed after oral administration with negligible first-pass effect and a high absolute bioavailability of approximately 100%, minimal CYP450 interaction, low (<15%) protein binding. Food does not affect rate and extent of absorption. The maximum LAC plasma concentrations occur approximately 1-4 hours post dose after oral dosing and elimination half-life is approximately 13 hours [91]. There is no published data in humans on LAC-alcohol interactions.

6.1.2 Dosage, Admin, Schedule

The manufacturer for lacosamide (LAC) (Vimpat®) has no involvement with the study. The Wellspring Compounding Pharmacy (WCP) in Oakland, CA is selected by the SFVAMC Research Pharmacy to compound placebo-controlled medications. WCP will obtain LAC from the manufacturer, and prepare 100 mg of LAC, 200mg capsules of LAC, and matching placebo. The SFVAMC Research Pharmacist will directly receive all study medications from WCP and store

appropriately. A single dose of either LAC 100 mg, LAC 200 mg or matching placebo will be given in each of the 3 Human Lab Sessions.

6.1.3 Method of Assignment/Randomization

Participants will be randomly assigned to one of 3 sequences for the 3 Human Lab ADP sessions, in a balanced within-subjects crossover design.

6.1.4 Blinding and Procedures for Unblinding

Matching study medications will be prepared by Wellspring Pharmacy and stored and dispensed by the SFVAMC Research Pharmacist. The Research Pharmacist will keep the randomization list. The investigators and participants will be blinded to the particular sequence of medication assignments.

6.1.5 Packaging/Labelling

The SFVAMC Research Pharmacist will manage these procedures: The Wellspring Compounding Pharmacy (WCP) in Oakland, CA is selected by the SFVAMC Research Pharmacy to compound placebo-controlled medications. WCP will obtain LAC from the manufacturer, and prepare 100 mg of LAC, 200mg capsules of LAC, and matching placebo. The SFVAMC Research Pharmacist will directly receive all study medications from WCP and store appropriately. A single dose of either LAC 100 mg, LAC 200 mg or matching placebo will be given in each of the 3 Human Lab Sessions.

6.1.6 Concomitant Therapy

Participants will be informed that they cannot use psychoactive drugs including antipsychotics, anxiolytics and antidepressants during the 30 days prior to entry, as well as anticonvulsants, beta blockers, central nervous system stimulants or depressants, or other drugs that cause excessive sedation in the judgment of the study physician/PI.

6.1.7 Restrictions

As per Exclusion Criteria, above.

6.2 Assessments

Please see the list of study measures below, Sec. 6.3.5

6.2.1 Efficacy

This is a pilot feasibility study, not an efficacy study. The primary outcome variables are measures of feasibility:

1. Time needed to recruit, screen, and run the study procedures for 4 participants.
2. Retention rates at the various in the study process (screening, Human Lab ADP session 1,2,3, and follow-up).
3. Adverse effects of study medication (lacosamide at 2 doses and placebo), before and after alcohol self-administration.

6.2.2 Safety

Please see the study procedures, below, Sec. 6.3.5, and steps to minimize risks, above, in Sec.3.3.5.

6.2.2.1 Adverse Events Definition and Reporting

Adverse Events

During the study, site personnel will note any change in the condition(s) and the occurrence and nature of any adverse events. For 7 days after the last dose of study supplement/placebo (post-discontinuation evaluation) participants will be closely followed for study drug-related adverse events in order to detect delayed toxicity. If drug-related toxicity is present beyond 7 days post last dose, participants will be followed every 7 days until the toxicity resolves, another therapy is initiated, or death. Important clinical information that comes to light during study participation will be communicated by research coordinators to the study physician in real time.

The study physician (either the PI, [name], or, in his absence, the study sub-I, [name]) will review each participant's safety at each study visit.

-Lab results will be reviewed on the same day that the results are received.

-Adverse effects reported by participants will be reviewed on the same day as they are reported by the study participant.

-Adverse effect assessment will be done by the research coordinators and discussed with the study physician on a daily basis, immediately after these adverse effects are reported by the participant to the study coordinator.

As with our current, CHR-approved clinical trials, the study physician, if not immediately present at the time of adverse effect data collection, will be contacted in real time by the study coordinator by phone, pager, or text message, so that adverse effects can be discussed with the study physician. The study physician, based on examination of the participant and/or review of the participant's data, will make a clinical judgment at each visit regarding whether it is safe to proceed with study medications.

The PI will report to the IRB, DSMB and study sponsor his assessment of the potential relatedness of each AE to protocol procedure, studied disease state, study drug via the CRF. For each adverse event recorded on the Adverse Event CRF, the PI will make an assessment of seriousness, severity, and causality.

According to the ICH guideline for Good Clinical Practice, an adverse event is any untoward medical occurrence in a clinical investigation participant administered a pharmaceutical product, regardless of causal attribution. An adverse event can therefore be any of the following:

- Any unfavorable and unintended sign (including an abnormal laboratory finding), symptom, or disease temporally associated with the use of a medicinal product, whether or not considered related to the medicinal product.
- Any new disease or exacerbation of an existing disease (a worsening in the character, frequency, or severity of a known condition).
- Recurrence of an intermittent medical condition (e.g., headache) not present at baseline.
- Any deterioration in a laboratory value or other clinical test (e.g., ECG, X-ray) that is associated with symptoms or leads to a change in study treatment or concomitant treatment or discontinuation from study drug. If a participant's dosage is reduced or treatment is discontinued as a result of an AE, the PI will report to the study sponsor via CRF the circumstances and data leading to any such dosage reduction or discontinuation of treatment.

Events leading to the clinical outcome of death from progressive disease will not be recorded as adverse events unless the PI believes that the event may have been caused by the study drug.

Serious adverse event (SAE) collection begins after the participant has signed informed consent and has received study drug. If a participant experiences an SAE after signing informed consent, but prior to receiving study drug, the event will NOT be collected unless the PI feels the event may have been caused by a protocol procedure.

The PI will alert the study sponsor of any SAE within 24 hours of the PI's awareness of the event. Alerts issued via telephone will be immediately followed with official notification on study-specific SAE forms.

An SAE is any adverse event from this study that results in one of the following outcomes:

- death (excluding death due to progression of study disease, unless related to study drug);
- initial or prolonged inpatient hospitalization;
- a life-threatening experience (that is, immediate risk of dying);
- persistent or significant disability/incapacity;
- congenital anomaly/birth defect;
- considered significant by the PI for any other reason.

Important medical events that may not result in death, be life-threatening, or require hospitalization may be considered serious adverse drug events when, based upon appropriate medical judgment, they may jeopardize the participant and may require medical or surgical intervention to prevent one of the outcomes listed in this definition.

Serious adverse events (SAEs) occurring after a participant has taken the last dose of study drug will be collected for 7 days after the last dose of study drug, regardless of the PI's opinion of causation. Thereafter, SAEs will not be reported unless the PI feels the events were related to either study drug, or drug delivery system, or a protocol procedure. Any SAE occurring prior to enrollment that the PI believes may have been caused by a protocol procedure will be reported to the study sponsor within 24 hours of the PI's awareness of the event and recorded on the CRF.

Study-specific clinical outcomes of death from progressive disease will be reported as SAEs only if the PI deems them related to use of the study drug.

Immediate Reporting Requirements From

PI to Sponsor:

Certain events will be immediately reported to allow the Sponsor to take appropriate measures to address potential new risks in a clinical trial. The PI will report such events to the Sponsor immediately; under no circumstances will be reporting take place more than 24 hours after the PI learns of the event. The following is a list of events that the PI will report to the Sponsor within 24 hours after learning of the event, regardless of relationship to study drug:

Serious adverse events

Non-serious adverse events of special interest

Pregnancies

The PI will report new significant follow-up information for these events to the Sponsor immediately (i.e., no more than 24 hours after becoming aware of the information). New significant information includes the following:

- New signs or symptoms or a change in the diagnosis;
- Significant new diagnostic test results;
- Change in causality based on new information;
- Change in the event's outcome, including recovery;
- Additional narrative information on the clinical course of the event.

Emergency Medical Contracts

Medical Monitor Contact Information:

Any life-threatening (i.e., imminent risk of death) or fatal AE that is attributed by the PI to the investigational product will be telephoned to the Medical Monitor immediately, followed by submission of written case details on an CRF within 24 hours.

The following is the contact information that will be utilized by the PI:

MEDICAL MONITOR

[name], MPH

SFVAMC/UCSF

[name]

[name]

[contact] [name]

Email: [contact]

Follow-up of Participants after Adverse Events

PI Follow-Up:

The PI will follow all unresolved treatment-related adverse event until the event has resolved to baseline grade or better, the event is assessed as stable by the PI, new therapy is initiated, the participant is lost to follow-up, or the participant withdraws consent.

Every effort will be made to follow all serious adverse events considered to be related to study drug or trial-related procedures until a final outcome can be reported. During the study period, resolution of adverse events (with dates) will be documented on the Adverse Event CRF and in the participant's medical record to facilitate source data verification (SDV). If, after follow-up, return to baseline status or stabilization cannot be established, an explanation should be recorded on the Adverse Event CRF.

Data Review - For Phase II or III Sponsor Studies

PIs will conduct continuous review of data regarding participant safety at weekly study group meetings where the results of each participant's treatment are discussed, as is currently done for the PI's other UCSF CHR approved clinical trials. The discussion will include the number of participants, significant toxicities as described in the protocol, doses adjustments, and observed responses.

6.3 Study Procedures

Identify all procedures considered experimental, those performed exclusively for research purposes and those that would occur regardless of the research (i.e. standard of care). Include all observations that will take place during the study, and

Study Schedule listing study procedures (visit by visit) with timing intervals to provide a summary for study team and reviewers.]

6.3.1 Study Schedule

STUDY VISIT	WEEK	TYPE OF VISIT	AMOUNT OF TIME
1	1	Baseline/screening	3 hours
2	2	Human lab session 1	12 hours
		Phone visit 1	10 minutes
	3	WASHOUT	
3	4	Human lab session 2	12 hours
		Phone visit 2	10 minutes
	5	WASHOUT	
4	6	Human lab session 3	12 hours
		Phone visit 3	10 minutes
5	7	Follow-up visit	1 hour
TOTAL		5 visits	40 hours and 30 minutes

6.3.2 Informed Consent

The process of informed consent will minimize undue influence or coercion and offer sufficient time for review. Typically study coordinators will receive thorough training on the correct way to conduct informed consent. On a rare occasion, a study physician or project manager will conduct informed consent. All staff conducting informed consents have at least a Bachelor of Arts or Science in a health-related field and/or have 2 years of research-related experience. Training for the administration of informed consent teaches study staff how to move through the consent, assessing participant's comprehension along the way. A staff member in training will (1) shadow a trained staff member conducting informed consent 2 times, then (2) practices informed consent with other lab members, and finally (3) conducts informed consent with a participant while another trained lab member watches. Once the staff member-in-training satisfactorily conducts informed consent under the supervision of another trained staff member, the staff-in-training becomes authorized to conduct informed consent.

6.3.3 Screening

After consent, participants will be scheduled for screening assessments. The screening phase is accomplished over a total of 1 to 2 visits.

6.3.4 Enrollment

[Identify who will enroll the subjects in the study and how this process will take place (for instance, after they have been consented, screened and meet eligibility criteria).]

6.3.5 On study visits

Baseline/screening visit	Patient Locator form
3 hours	Demographics
	Eligibility form
	Electrocardiogram (ECG)
	Medical History
	Physical Exam
	Lab tests
	Height/weight
	Concomitant Medications
	Concomitant Treatment Log
	Columbian Suicide Severity Rating Scale
	AE Checklist
	Breath alcohol test
	Structured Clinical Interview for DSM-5 (SCID)
	Timeline Followback (TLFB)
	Clinical Institute Withdrawal Assessment (CIWA-AD)

	Urine Drug Screen (UDS) Family Tree Questionnaire (FTQ) Barratt Impulsiveness Scale (BIS-11) Alcohol Use Disorders Identification Test (AUDIT) Vitals Balloon Analogue Risk Task (BART) Delay Discounting (DD)
Human Lab Sessions 1, 2 and 3 12 hours each human lab	Weight AE Checklist Concomitant Medications Approach Avoidance Task (AAT) Breath alcohol test Timeline Followback (TLFB) Clinical Institute Withdrawal Assessment (CIWA-AD) Urine Drug Screen (UDS) Blood alcohol level Vitals Alcohol Urge Questionnaire (AUQ) MD gait and body sway check Concomitant Treatment Digit Vigilance Test (DVT) Biphasic Alcohol Effects Scale (BAES) Yale Craving Scale – Short (YCS) Balloon Analogue Risk Task (BART) Delay Discounting (DD) Ratings of Drinking Behavior During the Alcohol Self-Administration Period
Phone visits 1, 2, and 3 10 minutes each phone call	AE Checklist Timeline Followback (TLFB)
Follow-up Visit 1 hour	Participant End of Study Questionnaire AE Checklist Breath alcohol test Timeline Followback (TLFB) Alcohol Urge Questionnaire (AUQ) Medical Management (MM)

Assessments at Study Entry and During and After Human Lab Sessions

At Entry:

These are adapted from previous/ current clinical studies at the UCSF/SFVAMC Addiction Research Program.

- Demographic data, will be assessed with data on age, race, socioeconomic status, marital status, educational and occupational levels, and significant medical history.
- A number of safety evaluations are included: Medical history and physical examination; Suicide Risk Assessment: The Columbia Suicide Severity Rating Scale [101]. It is a standard, thorough, frequently used method to screen for suicidal ideation, used by our group in alcohol use disorder clinical trials;
- Clinical Laboratory Tests for Health/Safety Monitoring: Blood samples will be collected for chemistry, liver panel, renal panel and complete blood count (CBC); urine will be collected for urinalysis and urine pregnancy tests on women of childbearing potential;
- ECG: an electrocardiogram will be performed to check cardiac conduction, in particular for PR interval prolongations, as this is of relevance to LAC, which can cause small, dose-related increases in mean PR interval
- Structured Clinical Interview for DSM-5, (SCID) [96]: the SCID will be used to determine DSM-V diagnosis of current (current year) Alcohol Use Disorder, and the DSM-V current psychiatric diagnoses for anxiety, mood, psychotic, and non-alcohol substance use disorders in order to determine study eligibility.
- Alcohol Use Disorders Identification Test (AUDIT): The AUDIT [97] is valid and reliable self-report measure of alcohol-related problem severity.
- Barratt Impulsiveness Scale (version 11) (BIS-11) [98]: This provides a trait measure of impulsiveness and will be used to characterize the study cohort at study entry.

- **Study Physician Review:** All health measures, medical history/exams and labs will be reviewed by a study physician to ensure that the subject meets all the eligibility criteria and are ready for randomization

At Entry and at various times throughout the study:

- **Clinical Institute Withdrawal Assessment for Alcohol, DSM-IV Version (CIWA-AD):** at entry and before each Human Lab Session and at each Follow-up;
- **Urine Drug Screen:** For opioids, benzodiazepines, cocaine, amphetamines, barbiturates: at entry and before each Human Lab Session;
- **Breath alcohol concentration (BrAlc):** at entry and before each Human Lab Session; and during each Human lab Session
- **Vital Signs:** Temperature, heart rate, and blood pressure will be measured at study entry and multiple times during each Human Lab Session.
- **Concomitant Medications Review:** at entry and before each Human Lab session: thorough review of all concomitant medications (prescription or over-the-counter) in the past 30 days, as well as those started during the study.
- **AE Checklist:** At Entry and at Human Lab Session 1, 2 and 3; Phone visits 1, 2, 3; 1-wk FU; The most commonly experienced side effects listed in the FDA package insert will be reviewed. Participants will be asked how many times they have experienced each side effect since the last study visit and severity.
- **Timeline Followback (TLFB):** at study entry, then Human Lab Session 1, 2 and 3; phone visits 1, 2 and 3. TLFB will be used to calculate standard drinks consumed per week in the past 30 days prior to consent and at the two Human Lab Sessions, and the 1-week follow-up. The TLFB will be used to determine whether subjects meet minimum alcohol consumption criteria at entry. Other substance use will also be collected by TLFB.
- **Balloon Analogue Risk Task (BART):** at each Human Lab session after medication
- **Delay Discounting:** at each Human Lab session after medication

At Follow-up visit:

- **Medical Management:** at the follow-up visit, research clinician will provide a motivational enhancement session to encourage the non-treatment seeking participants to consider treatment.

Measures of Alcohol Effects:

- **Breath alcohol concentration (BrAlc) [99] *at each visit, and multiple times in ADP Sessions 1 and 2.*** BrAlc will be measured at each session to detect recent alcohol use with the *Intoximeters Alco-Sensor IV* instrument.
- **Blood Alcohol Levels:** Human Lab Sessions 1 and 2 (Table 1): Blood samples will be drawn to measure plasma levels of blood alcohol (BAC) during the priming dose and during the alcohol self-administration paradigm. Blood samples will be stored at -4°C and will be analyzed at the San Francisco VA.
- **Biphasic Alcohol Effects Scale (BAES) [81]:** Human Lab Sessions 1 and 2 (Table 1). This 14-item self-report rating scale measures alcohol stimulant/ sedative effects and is used regularly in the Yale ADP.
- **Alcohol Urge Questionnaire (AUQ):** At study entry; multiple times in Human Lab Sessions 1 and 2 (Table 1); 1-wk FU; 1-mo FU: The AUQ is an 8-item questionnaire assessing *desire, expectation of positive effect, and inability to avoid drinking if alcohol is available.* The AUQ is a reliable and valid scale for the measurement of self-reported alcohol urges. Its brevity and time frame for ratings (i.e. right now) makes it suitable for the ADP.
- **Yale Craving Scale -Short (YCS):** Multiple times in Human Lab Sessions 1 and 2; visual analog scale that measures craving for alcohol
- **Ratings of Drinking Behavior During the Alcohol Self-Administration Period:** multiple times in Human Lab Sessions 1 and 2. Subjects will be videotaped during the alcohol self-administration portion of ADP 1 and ADP 2. Videotapes will be rated by two independent for the onset and offset of each sip of alcohol. Dependent measures will be constructed including time until the first sip and average time to consume each drink.
- **Vital Signs:** Human Lab Sessions 1 and 2 (Table 1). These will include heart rate, blood pressure, and skin. The blood pressure cuff will be on subject's dominant arm while the probe of will be attached to the middle finger of the subject's non-dominant arm. These data will be further used to examine the safety of using the study medications during alcohol self-administration.

Participant Incentives

STUDY VISIT	REIMBURSEMENT AMOUNT
Screening/baseline	\$85*
ADP Lab Session 1	\$224**
ADP Lab Session 2	\$224**
ADP Lab Session 3	\$224**

Follow-up visit	\$25
Bonus for completing ADP Sessions 1 + 2 + 3	\$50
Total	\$832

*At the screening/baseline visit, participants are paid per task they complete. At the end of screening, they will earn \$85.

**Participants will receive \$200 for each ADP Lab Session they complete. They could earn an additional \$24 per ADP Lab Session, depending on how many drinks they consume per session. At each session, participants are offered 8 drinks, each worth \$3. They will receive \$3 per drink for every drink that is not consumed.

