*****Protection against risks of medications*****

Effective screening will exclude participants who would be at greater risk for complications because of medical, neurological or psychiatric illnesses. Individuals currently dependent on other drugs will be screened out. Participants will be carefully monitored during each human laboratory session and will be given only single, observed doses of study medications. Participants will be educated of the risks attendant to study participation through the informed consent process.

Protection Against Risks of Lacosamide

Participants will take lacosamide only in an observed single dose administration by research staff. They will then be monitored closely from the time of medication administration at 8:30 until leaving the CRC at 8:00 PM.

Protection Against Effects of Lacosamide on Other Medications

To protect against this risk, we will do the following:

-The study physician will review all concomitant medications and determine whether there are potential drug interactions that need to be avoided.

-In the informed consent form, participants are instructed, "Lacosamide may cause a change (increase or decrease) in the effect of some other medications. If you are taking other medications during your participation in this study, immediately inform study staff. The study doctor will review any medications that you are taking and make the determination as to whether continued study participation is safe for you."

Blood Drawing (Venipuncture) Risks

Participation in the study requires participants to have their blood drawn 4 different times over the course of study (screening and human laboratory ADP sessions 1, 2, and 3). Having blood drawn may cause pain (common), fainting/passing out (not very often), a bruise where the needle goes in (not very often), and infection at the same place (rare).

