******Protection against unknown risks******

To protect against this risk, we will do the following:

- During the informed consent process, participants will be notified about the possibility of unknown risks associated with taking lacosamide or their combination with alcohol.
- During the informed consent process, the possibility of unknown risks are explained and that researchers will let participants know if new information about risks and side effects becomes available over the course of the study.
- Adverse effects will be carefully monitored during each ADP lab session.

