5.2.1 Primary Outcome Variables

The primary outcome variables are measures of feasibility:

1. Time needed to recruit, screen, and run the study procedures for 4 participants.
2. Retention rates at the various in the study process (screening, Human Lab ADP session 1,2,3, and follow-up).
3. Adverse effects of study medication (lacosamide at 2 doses and placebo), before and after alcohol self-administration.

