6.4.3.3 Safety

Descriptive statistics will be used to summarize the data. The AE checklist will be used to assess adverse effects. Descriptive statistics will be used.

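### Primary outcome 3 splits adverse effects at alcohol, but the AE checklist asks about everything back to the last study visit and has no stated onset item or in-session time

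*Combined protocol and SAP*

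**What the plan says.** Section 5.2.1 of the combined protocol and SAP defines the third primary outcome as "Adverse effects of study medication (lacosamide at 2 doses and placebo), before and after alcohol self-administration". Sections 6.2.1 and 6.4.3.1 repeat it. For the analysis, section 6.4.3.3 names one instrument: "The AE checklist will be used to assess adverse effects".

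Section 6.3.5 schedules the checklist at entry, at each of the three lab sessions, at each phone visit and at the 1-week follow-up. Its content is: "Participants will be asked how many times they have experienced each side effect since the last study visit and severity". The entry gives neither a position within the session nor an onset item. In the same list, the withdrawal assessment is placed before each session and vital signs are taken repeatedly during it. The checklist entry says neither.

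Other sections bear on events during a session:

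- Section 3.3.2, on participants given lacosamide: "They will then be monitored closely from the time of medication administration at 8:30 until leaving the CRC at 8:00 PM".
- Section 3.3.2, on unknown risks: "Adverse effects will be carefully monitored during each ADP lab session".
- Section 6.2.2.1: a study physician who is not present when adverse effects are collected "will be contacted in real time by the study coordinator by phone, pager, or text message".
- Section 6: on the day after each session, "a study staff member will call the participant to ask about well-being, assess for adverse effects and collect drinking data".

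Section 6.3.1 totals five visits. That total leaves out the three calls, although the same table labels each of them a phone visit.

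**The concern.** The outcome is meant to separate the effects of the drug alone from those of the drug with alcohol. The boundaries that matter are therefore the dose and the first drink. A question that runs back to the previous visit respects neither.

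The split matters in this trial. Feasibility and safety come first among the aims (4.2). Sections 3.3.2 and 6.1.1 report no published data on lacosamide with alcohol, and 3.3.2 expects that alcohol may increase dizziness and ataxia. The analysis is descriptive and 4 completers are planned, so events will be read one by one. That works only if each event's timing is on record, and timing not captured at the time is hard to reconstruct later.

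**Working it through.** The plan has no figure to reproduce here, since 6.4.1 rules out inferential statistics. The check is which periods the checklist reports can separate.

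**What the outcome needs.** 3 conditions × 2 periods = 6 summaries, each with counts and severity.

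**Periods in one session cycle.**
- W: off drug, from the previous contact to dosing
- PRE: dosing to first alcohol
- POST: first alcohol to discharge
- N: discharge to the next-day call

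**Case 1: one checklist per session.** Take the favourable reading first. The call counts as a visit, so the next window starts at the call, and the call's own window starts at the session checklist. Each cycle then gives two reports for four periods.

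| Checklist given | Session report covers | Call report covers |
|---|---|---|
| Before dosing | W | PRE + POST + N |
| After dosing, before alcohol | W + PRE | POST + N |
| After alcohol | W + PRE + POST | N |

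PRE never stands alone. The first row gives a total by dose but no split. The second gives an after-alcohol report (including the night after discharge), but PRE is merged with W. W runs back to screening at session 1 and to the previous call at sessions 2 and 3. The third row merges everything up to the checklist.

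**If the call does not count as a visit.** The session checklist then reaches back to the previous session. For the second row:

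session 2 report = POST₁ + N₁ + W₂ + PRE₂

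This mixes two study conditions. Subtracting the first call's count (POST₁ + N₁) leaves W₂ + PRE₂, which is still not PRE₂. Over three sessions there are 3 × 2 = 6 independent reports for 3 × 4 = 12 periods, and a rank check finds PRE unidentified at every placement.

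The start of the call's window matters as well. If it is taken to begin when the session ended, the call covers only N. The first row then loses its total by dose, and the second loses its after-alcohol report.

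**Case 2: checklist repeated in session, window as worded.** The pre-dose report covers W and the pre-drink report covers W + PRE. Counts can be subtracted if recall is consistent: (W + PRE) − W = PRE. Severity cannot. As a hypothetical example, a participant reports one headache, rated severe, before dosing, and two headaches, rated severe, before the drink. The PRE count is 2 − 1 = 1, but that headache could have had any severity up to severe.

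**Case 3: window reset at each checklist.** Checklists before dosing and before the priming drink, plus the call, report W, PRE and POST + N directly, with counts and severity. A further checklist at discharge would separate POST from N.

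**Other sources.**
- Section 6.2.2.1 has staff note the occurrence and nature of events. The only timing it mentions for the AE case report form is dates of resolution.
- Section 3.3.2 adds close monitoring, and gait and alertness tests through the day.
- Section 6.3.5 adds the BAES and vital signs.

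None of these is described as recording when a symptom began relative to the first drink, and none is named as the source for primary outcome 3.

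**The case against.** The strongest objection is that single administration is never stated. Section 6.3.5 lists the checklist once per session, but it also lists vital signs, breath alcohol, the AUQ and the Yale craving scale once, and all of these are described elsewhere in that section as repeated. A reader might infer from the listing that the checklist is given only once; the documents do not support that. This part of the objection stands, which is why Case 2 is needed. The recall wording still fails there.

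Second, the timing may exist out of sight. Section 6.3.5 refers other in-session measures to a Table 1 that is not in the text available, and the AE case report form is not visible. This also stands, although the checklist entry does not cite Table 1.

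Third, with few participants, known dosing and drinking times, staff present and real-time contact with the physician, an event reported live could be placed on either side of the first drink. Section 6.4.3.1 does not tie the outcome to the checklist exclusively. A reader might go further and infer that no before-and-after data can be collected at all. That is too strong. Staff notes could place some events, and gait, alertness, BAES and vital-sign measures cover impairment and sedation. They do not amount to a timed record of symptoms such as nausea, headache or diplopia.

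Last, a reader might gauge the damage by how small a share of the recall window is on drug before alcohol. That is a share of time and not of misplaced events. Section 6.1.1 puts peak concentration 1 to 4 hours after dosing, so effects need not be spread evenly over the window.

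**Conclusion.** The concern holds for the checklist as worded. Followed literally, it does not give adverse effects, with severity, for each condition on either side of alcohol. With one administration per session, the on-drug period before alcohol cannot be isolated. With repeated administrations, counts may be recoverable by subtraction, but severity by period in general is not. What can be recovered after alcohol, or by dose, depends on whether the call is a study visit and on where its window starts. The documents leave both open.

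One of three primary outcomes is affected. The documents do not support a number for how many events would be misplaced. The conclusion rests on three assumptions: the outcome is meant as a split into two periods, which is its natural reading; the checklist entry in 6.3.5 describes the instrument in full; and no timed symptom record sits in Table 1 or the AE case report form. If the last assumption is wrong, what remains is to cite that record and correct the recall wording.

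**What to change.** In 6.3.5, give the checklist at each lab session before dosing and again just before the priming drink. Make the recall window run from the last checklist, and state that the next-day call covers the time from the pre-drink checklist onward. Alternatively, record each event's onset time relative to dosing and first drink.

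In 6.4.3.1 and 6.4.3.3, name this as the source for primary outcome 3 and tabulate by dose and period. If Table 1 or the AE case report form already holds the timing, cite it there and correct only the recall wording.

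The cost is at most one or two extra short administrations per session. One extra is 1 × 3 sessions × 4 completers = 12, or 1 × 3 × 6 = 18 if all six possible starters attend every session. Two extra would double these to 24 and 36. The onset-time alternative costs one added field. Neither route needs a new instrument.
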